9.6.1.2 Serious Adverse Events

SAEs and treatment-related SAEs will be summarized separately by SOC and PT for the Run-In Safety Analysis Set and the Safety Analysis Set.

All SAEs recorded on the CRF will be listed for all screened subjects.

9.6.1.3 Adverse Events Leading to Discontinuation

A summary of AEs/TEAEs and treatment-related AEs/TEAEs leading to discontinuation (defined as an event with an outcome of 'drug withdrawn' in the CRF) will be provided, grouped by SOC and PT, for the Run-In Safety Analysis Set and the Safety Analysis Set. Supportive listings will be provided.

All AEs leading to discontinuation recorded on the CRF will be listed for the Run-In Safety Analysis Set and the Safety Analysis Set. Additionally, TEAEs leading to dose reduction will be listed for the Safety Analysis Set.

Additionally, TEAEs leading to dose reduction will be listed for the Safety Analysis Set

9.6.1.4 Deaths

A table presenting the number and percentage of subjects who died during the Run-In period and during the open-label treatment period will be presented for the Run-In Safety Analysis Set and Safety Analysis Set, respectively. Deaths occurring in the study will also be listed for all screened subjects.

9.6.1.5 Potentially Pertaining to Drug Withdrawal Symptoms

A summary of TEAEs potentially pertaining to drug withdrawal, as defined in [Appendix 2](#), will be summarized by SOC and PT for the Safety Analysis Set.

9.6.1.6 Potentially Pertaining to Pancreatitis

A summary of TEAEs potentially pertaining to pancreatitis, as defined in [Appendix 2](#), will be summarized by SOC and PT for the Safety Analysis Set.

9.6.1.7 Potentially Pertaining to Hepatic Disorders

A summary of TEAEs potentially pertaining to hepatic disorders, as defined in [Appendix 2](#), will be summarized by SOC and PT for the Safety Analysis Set.

9.6.1.8 Potentially Pertaining to Injection Site Reactions

A summary of TEAEs potentially pertaining to injection site reactions, as defined in [Appendix 2](#), will be summarized by SOC and PT for the Safety Analysis Set.

9.6.1.9 Potentially Pertaining to Respiratory Depression and Failure

A summary of TEAEs potentially pertaining to respiratory depression and failure, as defined in [Appendix 2](#), will be summarized by SOC and PT for the Safety Analysis Set.

9.6.1.10 Potentially Pertaining to Central Nervous System Depression

A summary of TEAEs potentially pertaining to central nervous system depression, as defined in [Appendix 2](#), will be summarized by SOC and PT for the Safety Analysis Set.

9.6.1.11 Potentially Pertaining to Orthostatic Hypotension

A summary of TEAEs potentially pertaining to orthostatic hypotension, as defined in [Appendix 2](#), will be summarized by SOC and PT for the Safety Analysis Set.

Sponsor: Indivior Inc.
Protocol no: RB-US-13-0003

9.6.2 Laboratory Data

Laboratory data will be reported using International System (SI) units as collected by the central laboratory. Unless otherwise specified, all continuous laboratory data will be summarized using descriptive statistics (n, mean, SD, median, min, and max) for each scheduled study assessment as well as change from baseline and percentage change from baseline [if applicable] by parameter class (hematology, chemistry, and urinalysis). The following parameters will have graphs of the mean values by visit through the end of study: hematocrit, alkaline phosphatase (ALP), alanine aminotransferase (ALT), amylase, lipase, trypsinogen, aspartate aminotransferase (AST), creatinine clearance, creatinine kinase, gamma-glutamyl transferase, and bilirubin (from serum chemistry results). All laboratory assessments include a baseline summary as defined in [Section 5](#) unless otherwise indicated. Hematology, chemistry, and urinalysis data will be summarized by displaying shifts from baseline value (low/normal/high) to last assessment on treatment and worst result on treatment (for only subjects with normal as baseline) considering both scheduled and unscheduled assessments. All laboratory assessments will be listed by panel with the corresponding normal ranges for each parameter. Screening laboratory will be provided in a separate listing.

9.6.2.1 Hematology

Parameters include hematocrit, hemoglobin, mean corpuscular hemoglobin, mean corpuscular hemoglobin concentration, mean corpuscular volume, platelet count, pancreatic enzymes, absolute red blood cell count, and absolute white blood cell count. Visits include Week 1 Day 1, Week 3 Day 15, Week 5 Day 29, Week 7 Day 43, Week 9 Day 57, Week 11 Day 71, Week 13 Day 85, Week 15 Day 99, Week 17 Day 113, Week 19 Day 127, Week 21 Day 141, Week 25 Day 169, Week 29 Day 197, Week 33 Day 225, Week 37 Day 253, Week 41 Day 281, Week 45 Day 309, Week 49 Day 337, and end of study visit.

9.6.2.2 Serum Chemistry

Parameters include albumin, ALP, ALT, amylase, AST, blood urea nitrogen, calcium, calculated creatinine clearance, carbon dioxide, chloride, creatinine, creatinine kinase and subtypes, gamma-glutamyl transferase, globulin, glucose (non-fasting), high-density lipoprotein, immunoreactive trypsinogen, lactate dehydrogenase, lipase, low-density lipoprotein, magnesium, phosphorus, potassium, sodium, total bilirubin, direct bilirubin, total cholesterol, total protein, triglycerides, and uric acid. Visits include Week 1 Day 1, Week 3 Day 15, Week 5 Day 29, Week 7 Day 43, Week 9 Day 57, Week 11 Day 71, Week 13 Day 85, Week 15 Day 99, Week 17 Day 113, Week 19 Day 127, Week 21 Day 141, Week 25 Day 169, Week 29 Day 197, Week 33 Day 225, Week 37 Day 253, Week 41 Day 281, Week 45 Day 309, Week 49 Day 337, and end of study visit.

An additional summary of potential hepatotoxicity will be presented with the number and percentage of subjects at each time point and at any point on study that meet the following conditions: $ALT > 3 \times$ upper limit of normal (ULN), $ALT \geq 3 \times$ ULN to $< 5 \times$ ULN, $ALT \geq 5 \times$ ULN to $< 8 \times$ ULN, $ALT \geq 8 \times$ ULN, $AST > 3 \times$ ULN, $AST \geq 3 \times$ ULN to $< 5 \times$ ULN, $AST \geq 5 \times$ ULN to $< 8 \times$ ULN, $AST \geq 8 \times$ ULN, $ALT > 3 \times$ ULN and $AST > 3 \times$ ULN, ALT and $AST \geq 3 \times$ ULN to $< 5 \times$ ULN, ALT and $AST \geq 5 \times$ ULN to $< 8 \times$ ULN, ALT and $AST \geq 8 \times$ ULN, $Bilirubin \geq 2 \times$ ULN, $Bilirubin \geq 2 \times$ ULN to $< 5 \times$ ULN, $Bilirubin \geq 5 \times$ ULN Hy's Law cases which is defined as $AST > 3 \times$ ULN or $ALT > 3 \times$ ULN, $bilirubin > 2 \times$ ULN, and $ALP < 2 \times$ ULN, and Modified Hy's Law which is defined as $AST > 3 \times$ ULN **AND** $ALT > 3 \times$ ULN, $bilirubin > 2 \times$ ULN, and $ALP < 2 \times$ ULN. A listing of these cases including the results for the parameters and the number of times the ULN each result is will be provided. Figures of $ALT [\times$ ULN] vs. total bilirubin $[\times$ ULN] and $AST [\times$ ULN] vs. total bilirubin $[\times$ ULN] on a log/log scale and box plots of AST , ALT , and total bilirubin will be presented

An additional summary of high values of amylase, lipase, and trypsinogen will be presented with the number and percentage of subjects at each time point and at any point on study that meet the following conditions: $Amylase > 3 \times$ upper limit of normal (ULN), $Lipase > 3 \times$ ULN, and $Trypsinogen > ULN$. A listing of these cases including the results for the parameters and the number of times the ULN each result is will be provided.

Sponsor: Indivior Inc.
Protocol no: RB-US-13-0003

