### 4.2 Inclusion Criteria

A. **De novo Subjects:** Subjects who have not participated in Study RB-US-13-0001 must meet the following criteria to be enrolled in this study:

1. Subjects seeking treatment for opioid use disorder who currently, and by medical history over the previous 3 months, meet the DSM-5 criteria for moderate or severe opioid use disorder.
2. Subjects who provide written informed consent to participate in this study.
3. Subjects who are an appropriate candidate for opioid partial-agonist treatment in the opinion of the Investigator or medically responsible physician.
4. Either male or female.
5. Age  $\geq 18$  to  $\leq 65$  years.
6. Have a body mass index (BMI) of  $\geq 18.0$  to  $\leq 35.0$  kg/m^2.
7. **Females:** Women of childbearing potential (defined as all women who are not surgically sterile or postmenopausal for at least 1 year prior to informed consent), must have a negative pregnancy test prior to enrollment and must agree to use a medically acceptable means of contraception from screening through at least 6 months after the last dose of investigational medicinal product (IMP).

**Males:** Subjects with female partners of child-bearing potential must agree to use medically acceptable contraception after signing the informed consent form (ICF) through at least 6 months after the last dose of IMP. Male subjects must also agree not to donate sperm during the study and for 6 months after receiving the last dose of IMP.

The following methods of contraception are considered to be medically acceptable: established use of oral, injected or implanted hormonal contraception; placement of an intrauterine device or intrauterine system; use of a double-barrier method of contraception (condom or occlusive cap with use of a spermicide) or male sterilization.

8. Subjects must agree not to take any buprenorphine products other than those administered during the current study throughout participation in the study.
9. Subjects must be willing to adhere to study procedures.

B. **Roll-Over Subjects:** Subjects who have successfully completed Study RB-US-13-0001 in its entirety must complete EOS/Day 169 assessments, which will serve as screening for this study. In addition, **only** the following criteria must be met to be enrolled in this study:

1. Provide written consent to participate in this study.
2. Be considered eligible in the medical judgment of the Investigator.

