14. History or presence of allergic or adverse response (including rash or anaphylaxis) to buprenorphine, naloxone, or the ATRIGEL Delivery System.
15. Total bilirubin  $\geq 1.5$ x the upper limit of normal (ULN), alanine aminotransferase (ALT)  $\geq 3$ xULN, aspartate aminotransferase (AST)  $\geq 3$ xULN, serum creatinine  $> 2$ xULN, international normalized ratio (INR)  $> 1.5$ xULN, lipase  $> 3$ xULN, amylase  $> 3$ xULN, or any abnormal pancreatic enzyme value above ULN that is associated with clinically significant, active pancreatic disorder.
16. Congenital long QT syndrome, history of prolonged QT in the 3 months prior to screening, or a corrected QT interval (Fridericia's – QTcF)  $> 450$  msec (male) or  $> 470$  msec (female) or history of risk factors for Torsades de Pointes.
17. Diagnosis of acquired immunodeficiency syndrome (AIDS).
18. Affiliated with, or a family member of, site staff directly involved in the study.
19. Unable, in the opinion of the Investigator or the medically responsible physician, to comply fully with the study requirements.
20. Clinically significant anemia or low hemoglobin (levels  $< 9$  g/dL) at Screening.
21. Donation of  $> 250$  mL of blood or plasma within the 30 days prior to providing written informed consent
22. Participation in any other clinical trial within 30 days prior to informed consent
23. Received medication-assisted treatment for opioid use disorder (e.g., methadone, buprenorphine) in the 90 days prior to providing written informed consent
24. Previously received RBP-6000.
25. Use of (within the past 30 days prior to providing written informed consent) or positive UDS result at screening for barbiturates, benzodiazepines, or methadone.

**B. Roll-Over Subjects** who meet any of the following criteria will be excluded from the study:

1. Discontinued early from Study RB-US-13-0001
2. Experienced any major protocol deviations or adverse events during the RB-US-13-0001 study which, in the opinion of the Investigator, could potentially compromise subject safety.
3. Women of childbearing potential who have a positive pregnancy test at EOS/Day 169, who are pregnant or breastfeeding, seeking pregnancy, or failing to use adequate contraceptive methods during the study.

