9.0 Statistical Methods

All statistical analyses will be performed using SAS® Version 9.4 or higher.

Categorical variables will be summarized using counts and percentages. Percentages will be rounded to one decimal place; except 100% will be displayed without any decimal places and percentages will not be displayed for zero counts. When assessments are not applicable (ie Post injection 6 visits for roll-over subjects), an N/A will displayed instead of a zero,

Sponsor: Indivior Inc.
Protocol no: RB-US-13-0003

Continuous variables will be summarized using the number of observations (n), mean, standard deviation (SD), median, minimum, and maximum. The minimum, maximum, and 95% CI values (in some instances) will be displayed to the same level of precision as the raw data, the median and mean to one additional decimal place and the SD to two additional decimal places. The maximum number of decimal places will be 4. All summaries will be presented by subject type (de novo or roll-over) unless otherwise stated.

Unless otherwise stated, summaries will be presented by subject type (de novo or roll-over and total). Missing values will be presented by blank spaces. For partially missing dates, the information present will be printed; e.g., "--JAN2000".

For dichotomous outcome measures such as urine drug screen results (negative; non-negative) and self-reports for illicit opioid use (negative; non-negative), any missing observation will be set equal to "non-negative." Missing results for substances other than opioids will not be imputed. For all continuous endpoints (e.g., COWS, SOWS, and VAS), the missing data will not be imputed.

Only scheduled assessments per protocol Amendment 4 will be presented in tables and figures except for worst case post-baseline and at any time types of analyses (all post-baseline including unscheduled assessments data will be considered for this derivation) but all data will be presented in the listings.

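### The liver and pancreas threshold counts in SAP 9.6.2.2 ignore baseline, so elevations already present at Day 1 that persist or recur are not separated from new ones

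*SAP*

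**What the plan says.** - SAP 9.6.2.2, liver: "An additional summary of potential hepatotoxicity will be presented with the number and percentage of subjects at each time point and at any point on" the trial. The rows cover ALT and AST above 3×ULN and in bands up to 8×ULN and over, bilirubin from 2×ULN, and Hy's Law combinations. The rule does not refer to the subject's baseline value.
- SAP 9.6.2.2, pancreas: "An additional summary of high values of amylase, lipase, and trypsinogen will be presented". The rows are amylase and lipase above 3×ULN and trypsinogen above ULN, again by time point and at any point, again with no baseline condition.
- SAP 9.0 describes the data behind such counts: "at any time types of analyses (all post-baseline including unscheduled assessments data will be considered for this derivation". It also presents summaries by subject type and total.
- SAP 9.6.2 plans shift tables in low/normal/high categories, to the last assessment and to the "worst result on treatment (for only subjects with normal as baseline".
- SAP 5.0 sets baseline as the last value before the Day 1 injection of this study. It also says that adverse events ongoing at roll-over are not treatment-emergent.
- Protocol 4.3, list A item 15 (A15) excludes de novo subjects with bilirubin from 1.5×ULN, ALT or AST from 3×ULN, lipase or amylase above 3×ULN, "or any abnormal pancreatic enzyme value above ULN that is associated with clinically significant, active pancreatic disorder".
- For roll-overs, Protocol 4.2 B says that only "the following criteria must be met to be enrolled in this study", and the list has no laboratory limit. Of the three exclusions in 4.3 B, none is a laboratory limit; the nearest is "Experienced any major protocol deviations or adverse events during the RB-US-13-0001 study which, in the opinion of the Investigator, could potentially compromise subject safety".

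**The concern.** Laboratory change is a primary variable (SAP 4.1), and hepatic and pancreatic events are adverse events of special interest (SAP Appendix 2). In an open-label study with no control arm, a table of potential hepatotoxicity will be read as the rate at which liver abnormalities arise on RBP-6000. A count that ignores baseline answers a different question: how many subjects had such a value after Day 1, whether or not they had it before.

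Entry elevations are plausible in this population. Protocol 1.1 links many hepatitis C cases to injection drug use. The film label in Protocol Appendix 7 names pre-existing enzyme abnormalities and viral hepatitis as possible contributors to hepatic events on buprenorphine.

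The SAP is also uneven. An ALT-increase adverse event ongoing at roll-over that does not worsen is left out of the treatment-emergent tables. The laboratory value behind it, if it persists, is counted in 9.6.2.2.

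**Working it through.** The plan has no figure to reproduce here: Protocol 9.2 has no formal sample size calculation, and no entry rate is given. The check is of the counting rule.

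**1. Who can be above a threshold at Day 1?**

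| Threshold in SAP 9.6.2.2 | De novo | Roll-over |
|---|---|---|
| ALT, AST >3×ULN | Excluded at screening (A15) | No numeric limit |
| Bilirubin ≥2×ULN | Excluded at screening (A15, from 1.5×ULN) | No numeric limit |
| Amylase, lipase >3×ULN | Excluded at screening (A15) | No numeric limit |
| Trypsinogen >ULN | Excluded only with an active pancreatic disorder | No numeric limit |

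De novo screening is on Days -21 to -15 (Protocol Appendix 1), before the film run-in. A de novo subject can therefore still cross a threshold by Day 1. The gap is wider for roll-overs but not confined to them.

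**2. What does the any-point count do?** With SAP 9.0 applied:
- elevation seen only at baseline: adds 0;
- elevation at baseline that persists or recurs afterwards: adds 1;
- new elevation after baseline: adds 1.

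The last two cannot be told apart in the count.

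**3. Can another planned output separate them?**
- The by-time-point table starts at Week 1 Day 1, when blood is drawn before injection (Protocol Appendix 2). It shows how many were above the threshold at entry. That number cannot be subtracted from the any-point count, because some entry elevations resolve.
- In the shift tables, 1.1×ULN and 8×ULN are both high. The worst-result shift is limited to subjects normal at baseline, so a rise from 1.5×ULN to 6×ULN, a genuine new case above 3×ULN and 5×ULN, is outside it.
- The listings give each result as a multiple of ULN. The split can be rebuilt by hand from them, but no summary reports it.

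**4. How large could it be?** Inputs: N = 300 roll-overs (planned, Protocol 3.1). Assumptions, not from the documents: b = share above 3×ULN at baseline; r = share of those above it again after baseline because of the same elevation; e = rate of new elevation.

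Planned count = N × [b·r + b·(1 − r)·e + (1 − b)·e]

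Count among those below the threshold at baseline = N·(1 − b)·e out of N·(1 − b), which is e.

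| b | r | e | Planned count | Planned rate | New-onset rate | Pre-existing cases counted (N·b·r) |
|---|---|---|---|---|---|---|
| 0 | any | 2% | 6.0 | 2.0% | 2.0% | 0 |
| 5% | 0 | 2% | 6.0 | 2.0% | 2.0% | 0 |
| 1% | 1 | 2% | 8.9 | 2.98% | 2.0% | 3 |
| 3% | 0.5 | 2% | 10.4 | 3.47% | 2.0% | 4.5 |
| 5% | 1 | 2% | 20.7 | 6.9% | 2.0% | 15 |
| 5% | 1 | 5% | 29.2 | 9.75% | 5.0% | 15 |

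For the fifth row: 300 × (0.05 + 0 + 0.95 × 0.02) = 300 × 0.069 = 20.7.

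**The case against.** The other side has good points.

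- A reader might infer that every abnormality present at roll-over entry appears as hepatotoxicity. It does not: SAP 9.0 keeps baseline values out of the any-time counts, so only elevations that persist or recur matter.
- A reader might infer that a roll-over with a grossly raised ALT gets in automatically. Protocol 4.2 B also requires the investigator to judge the subject eligible, and 4.3 B removes those whose earlier adverse events could compromise safety. These are judgments rather than numeric caps, but they are screens.
- A reader might infer that entry elevations in roll-overs are unrelated to the drug. Protocol 1.5 shows that RB-US-13-0001 had RBP-6000 arms, so some may follow earlier exposure. Counting those is cautious, and it is a reason to keep the planned count.
- A reader might infer a biased comparison of roll-over with de novo subjects. The SAP plans no test between them, and they differ anyway in exposure (6 against up to 12 injections).
- The Day 1 row, the case listings and the normal-at-baseline shift already show part of the picture. The table shells are in a separate document that is not available here, so extra rows or footnotes there cannot be ruled out.

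All of this narrows the point. What stands is that no summary in the SAP text gives new cases at 3×, 5× or 8×ULN given the baseline multiple, and the Day 1 row cannot supply them.

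**Conclusion.** The point holds in a limited form. The threshold counts mix new elevations with Day 1 elevations that persist or recur. Either subject type can be affected, roll-overs more because A15 does not apply to them.

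The size cannot be determined from the documents. Over the assumed ranges (b from 0 to 5%, r from 0 to 1, 300 roll-overs) the pre-existing cases in the count run from 0 to 15, and the reported rate runs from no change to 6.9% against a true 2.0%, or 9.75% against 5.0%. It is zero if nobody enters above a threshold or no entry elevation persists. The documents do not support quoting any particular fold difference between the two columns.

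No figure in the plan is wrong. This is a worthwhile, inexpensive improvement to a primary safety output.

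**What to change.** In SAP 9.6.2.2:

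1. State that any point on study means post-baseline, scheduled and unscheduled, in line with SAP 9.0.
2. Keep the planned counts.
3. For each ALT, AST, bilirubin, amylase, lipase and trypsinogen threshold, add by subject type and total the number and percentage newly meeting it, with subjects who did not meet it at the Day 1 baseline as denominator. A baseline-by-worst shift table in multiples of ULN would serve equally well. It also handles the banded rows, where a subject falling from a higher band should not count as new in a lower one.
4. Show alongside the number already above the threshold at baseline.
5. Footnote that A15 applied to de novo subjects only, and that some roll-over elevations may follow RBP-6000 given in RB-US-13-0001.

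The cost is a few extra rows in two planned tables, from data already collected. Eligibility, visits and care do not change.

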3.0 Study Design

This is a multicenter, open-label, long-term Phase III safety study in which approximately 600 subjects diagnosed with opioid use disorder will be enrolled (approximately 300 subjects who did not participate in the RB-US-13-0001 study [hereafter referred to as “*de novo*” subjects] and approximately 300 subjects that completed the RB-US-13-0001 study [hereafter referred to as “roll-over subjects”]). Subject participation will be based on the Investigator’s determination that initiation or continuation of study treatment is appropriate; and, that among subjects who are continuing from the RB-US-13-0001 study, there have been no significant protocol deviations or clinically important AEs that would preclude inclusion of the subject in RB-US-13-0003.

Before receiving the first injection of RBP-6000 in this safety study, all subjects will undergo a Run-In period with SUBOXONE® (buprenorphine/naloxone) sublingual film to avoid precipitating a withdrawal syndrome and to preserve blind in subjects treated with placebo in the RB-US-13-0001 study. Subjects will be inducted onto SUBOXONE sublingual film consistent with the SUBOXONE sublingual film label; they will then complete a 1 to 11 day SUBOXONE sublingual film Dose Adjustment period.

Once subjects meet the criteria (on Day -11 to Day -1) of no significant opioid craving (≤ 20 mm on the Opioid Craving VAS and no significant withdrawal (≤ 12 on the COWS) they may receive the first SC injection of RBP-6000 (containing 300 mg of buprenorphine). Subjects with significant withdrawal signs/symptoms (defined as > 12 on the COWS) or significant cravings for opioids (defined as > 20 mm on the Opioid Craving VAS) after the end of the 2-week SUBOXONE sublingual film Run-In period will not be eligible to continue in the study and will be referred for treatment.

On Day 1 of the study (initiation of study drug injections), all subjects will receive a SC injection of 300 mg of buprenorphine in RBP-6000. Subsequent doses of RBP-6000 may be adjusted down to 100 mg and back up to 300 mg based on the medical judgment of the Investigator. After injection of RBP-6000, subjects will not be permitted to receive supplemental SUBOXONE sublingual film during the RBP-6000 treatment period. Subjects who require supplemental SUBOXONE sublingual film or other sublingual buprenorphine pharmacotherapy during the RBP-6000 treatment period will be withdrawn from the study and referred for appropriate treatment.

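### The combined ALT-and-AST severity rows count only subjects with both enzymes in the same band, so the hepatotoxicity table gives no count of subjects with both at or above 5×ULN

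*SAP*

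**What the plan says.** SAP 9.6.2.2 (Serum Chemistry) introduces the table so: "An additional summary of potential hepatotoxicity will be presented with the number and percentage of subjects at each time point and at any point". The conditions listed there include:

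- for each enzyme separately, a row above 3×ULN and three bands (≥3 to <5, ≥5 to <8, ≥8×ULN);
- one ungraded joint row, ALT and AST both above 3×ULN;
- three graded joint rows: "ALT and $AST \geq 3 \times$ ULN to $< 5 \times$ ULN", then "ALT and $AST \geq 5 \times$ ULN to $< 8 \times$ ULN, ALT and $AST \geq 8 \times$ ULN";
- bilirubin rows, and Hy's Law and modified Hy's Law rows built on thresholds of 3×ULN for the transaminases.

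The section adds: "A listing of these cases including the results for the parameters and the number of times the ULN each result is will be provided". It has no rule for a subject whose two enzymes fall in different bands, and it does not say whether the ALT and AST values must come from the same sample. Laboratory changes are among the primary variables in SAP 4.1.

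**The concern.** The graded joint rows follow directly after the ungraded joint row and reuse the single-enzyme cut-points. A reader will naturally take them as the severity breakdown of the joint elevations, and will add the upper two to learn how many subjects had both enzymes at 5×ULN or more. That sum is wrong whenever the two enzymes straddle a cut-point. ALT 9×ULN with AST 6×ULN has both enzymes above 5×ULN yet meets none of the three graded conditions. Neither does ALT 7.9 with AST 8.0, where the two values are almost equal. In a study whose primary purpose is safety, the reported grading of joint transaminase elevation could then look milder than the data.

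**Working it through.** **Reproduction.** The documents state no figure for this point, so there is none to reproduce. The check is an enumeration of the rows.

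**Step 1: the grid.** Inputs are the cut-points 3, 5 and 8×ULN from SAP 9.6.2.2. At one time point, with both enzymes at least 3×ULN:

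| | AST 3 to <5 | AST 5 to <8 | AST ≥8 |
|---|---|---|---|
| ALT 3 to <5 | graded row 1 | none | none |
| ALT 5 to <8 | none | graded row 2 | none |
| ALT ≥8 | none | none | graded row 3 |

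Both at least 3×ULN: 3 × 3 = 9 cells, 3 covered, 6 not. Both at least 5×ULN: 2 × 2 = 4 cells, 2 covered, 2 not. Both at least 8×ULN: 1 cell, covered.

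**Step 2: can the count be recovered from the other rows?** Take two constructed pairs of subjects at one visit, values in ×ULN, bilirubin normal throughout.

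| | Subject 1 (ALT, AST) | Subject 2 (ALT, AST) |
|---|---|---|
| Scenario A | 9, 6 | 4, 1 |
| Scenario B | 9, 1 | 4, 6 |

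Both scenarios fill the table identically: ALT >3, two; ALT 3 to <5, one; ALT ≥8, one; AST >3, one; AST 5 to <8, one; ALT and AST both >3, one; graded joint rows, 0, 0 and 0. Scenario A has one subject with both enzymes at least 5×ULN and scenario B has none. The rows therefore do not determine that count. Only the listing does, subject by subject.

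**Step 3: possible size, on assumptions that are not in the documents.** ALT and AST in ×ULN were taken as bivariate log-normal at a single assessment, with common median 0.6 or 1.0, log-SD 0.6, 0.8 or 1.0, and correlation 0.7, 0.8, 0.9 or 0.95. That is 2 × 3 × 4 = 24 settings, with 2,000,000 simulated pairs each. The share missed is P(bands differ | both at least k). The expected number missed is 600 × P(both at least 5 and bands differ), where 600 is planned enrolment (SAP 3.0: "approximately 600 subjects diagnosed with opioid use disorder will be enrolled").

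| Median, log-SD, correlation | Per 600, both ≥5 | Share missed | Per 600, missed |
|---|---|---|---|
| 0.6, 0.6, 0.7 | 0.01 | 33% | 0.00 |
| 0.6, 0.8, 0.8 | 0.77 | 32% | 0.24 |
| 1.0, 1.0, 0.9 | 20.78 | 32% | 6.73 |

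Over all 24 settings the missed share was 9% to 54% among pairs with both at least 3×ULN, and 10% to 42% among pairs with both at least 5×ULN. The expected number missed at the higher level ran from 0.00 to 6.73 per 600. Shares in the lowest settings rest on few simulated pairs and are imprecise.

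**Step 4: the any-point column.** A subject discordant at one visit may be concordant at another and enter a graded row that way. The omission in steps 1 and 2 is therefore certain at a given time point, but need not persist in the any-point column.

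**The case against.** The strongest reply is that nothing is hidden. The ALT 9, AST 6 subject counts in the joint row above 3×ULN, in the ALT ≥8 row and in the AST 5 to <8 row, and is listed with both multiples. Both Hy's Law definitions use the 3×ULN threshold and are untouched. The SAP never says that the graded rows add up to the ungraded one. The table is descriptive, and no test or stopping rule depends on it. The row layout may be refined in the table shells, which SAP Appendix 3 places in a separate document that was not available for this review. All of that stands and limits the consequence. It does not supply a count of subjects with both enzymes at 5×ULN or more, as step 2 shows.

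Three stronger readings are tempting, and the documents do not support them.

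- *Many subjects with both enzymes at least 5×ULN are missed.* Neither document gives any frequency of raised enzymes, and only one pattern is affected at that level. Protocol 4.3 also excludes de novo subjects with ALT or AST at 3×ULN or more at screening, which the simulation ignores.
- *The loss is worst among the most severe.* Pairs with both enzymes at least 8×ULN are always counted. In the middle setting of step 3 the missed share was 37% with both at least 3×ULN and 32% with both at least 5×ULN. It was lower at the higher level in 21 of the 24 settings. The other three each expected fewer than 0.1 subject per 600 with both at least 5×ULN.
- *The any-point column double counts.* A subject at 4×ULN at one visit and 9×ULN at another did meet both conditions on study. Counting that subject in both bands follows the stated rule. Classifying by peak value instead is a display choice.

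**Conclusion.** The concern holds as a defect in a stated tabulation rule. At any time point, a subject with both enzymes above 3×ULN in different bands is in no graded joint row. This includes every subject with one enzyme at 5 to <8×ULN and the other at ≥8×ULN. The upper two joint rows can both be zero while subjects with both enzymes at least 5×ULN exist, and the table has no other row that reveals them.

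This rests on reading the conditions literally and on the unseen shells not adding a rule for discordant pairs. The structural result (6 of 9 and 2 of 4 combinations uncovered) needs no distributional assumption. The number of subjects does: it is unknown and may be small. On the assumed distributions it is between about 0 and 7 of 600 at one assessment. What is missing is the joint severity split, not the subjects themselves.

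**What to change.** In SAP 9.6.2.2, replace the three joint interval rows with cumulative rows on values from the same sample: ALT and AST both ≥3×ULN, both ≥5×ULN, both ≥8×ULN. Each row then answers its own question, and all nine combinations are covered. Alternatively, keep the bands but assign each sample by the lower of the two multiples, so that at a time point every pair with both at least 3×ULN falls in exactly one band. State the same-sample requirement in the text and carry the definition into the table shells. While editing, use one boundary at 3×ULN: a value of exactly 3 meets the ≥3 band but not the >3 row. The cost is SAP wording and a change to one table program. No new data, visits or assessments are needed.
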